8.5 Preparation and labelling of Investigational Medicinal Product

Labels for aspirin (aspirin lysine) and ticagrelor will be prepared in accordance with Good Manufacturing Practice and regulatory guidelines of the Medicines Healthcare and Regulatory Agency. The label will include the following information: drug, formulation, dose, and dosing frequency as well as other information to comply with annex 13.

Participants will also be given written, illustrated dose-preparation instructions for aspirin (aspirin lysine) as described elsewhere in this protocol.

8.6 Dosage schedules

The dosage schedules are described in section 7.3, 7.7 and the trial flow chart within this protocol.

When taking once-daily doses of study medication, this will be on waking, with the exception of the endotoxin injection days when they will be asked to delay taking until the appropriate point within the study visit. When taking twice-daily, this should be on waking (with the exception of the endotoxin injection days when they will be asked to delay taking until the appropriate point within the study visit) and then as close to 12 hours later as possible.

In the case of a missed dose, the participant will be advised to take the dose when they remember if within 6 hours (twice-daily regimens) or 12 hours (once-daily regimens) of the intended time, otherwise to wait to take the next dose on time. In the event of vomiting after a dose, they should wait for the next dose before taking the study medication again in order to avoid accidental overdose.

The doses of aspirin (aspirin lysine) and ticagrelor will not be adjusted for any parameter. The maximum duration that a participant will receive aspirin (aspirin lysine) will be 28 days and ticagrelor 1 day.

8.7 Dosage modifications

Discontinuation of aspirin (aspirin lysine) and/or withholding ticagrelor may be considered in the following circumstances:

Major bleeding, including life-threatening bleeding

Intolerable adverse reaction such as minor bleeding that cannot be controlled by local measures

Discovery of severe thrombocytopenia (platelet count < 50,000/µL)

No dose adjustment beyond that specified by the randomisation schedule will be permitted.

8.8 Known drug reactions and interaction with other therapies

Details are to be found in section 8.9 below, in the current SmPCs for aspirin (aspirin lysine) and ticagrelor orodispersible tablets.

8.9 Concomitant medication

Regular concomitant medication will lead to exclusion from randomisation. Recording of any prescribed or over-the-counter medication after randomisation will be made at each subsequent visit. If at visits 3 and 7, any of the criteria in section 7.10 are met, the participant will be withdrawn if the visit cannot be postponed. Similarly, if at visit 6 the criteria in section 6 are not met, the participant will be withdrawn if the visit cannot be postponed. All individual medications, prescription and over-the-counter, will be recorded peri-event for any SAE or discontinuation due to AE. The following should be observed if any participant receives concomitant medication after randomisation:

Oral antiplatelet therapies

Aspirin (acetylsalicylic acid): Aspirin use, with the exception of the study medication as prescribed, is prohibited during the study period. At enrolment, patients will be asked to not use aspirin as an analgesic and they will be made aware of the range of over-the-counter products that contain it. If no contraindication exists, paracetamol will be recommended if the need for analgesia arises, but endotoxin injection should not be performed if paracetamol has been received in the preceding 24 hours. Patients will be asked about extra aspirin use, including over the counter supplies, at all visits. If, during the course of study treatment, a participant develops a clinical indication for regular antiplatelet therapy, a clinically appropriate regimen will be prescribed and they will be followed up but withdrawn from the study. Participants who receive at least one dose of IMP or endotoxin will be followed up by telephone 10-14 days after withdrawal.

Other oral antiplatelet therapies: Treatment with any other oral antiplatelet therapy apart from the study medication (e.g. clopidogrel, prasugrel, dipyridamole, cilostazol) is prohibited during the course of study medication. However, if during the course of study treatment, a participant develops a contraindication to

aspirin or ticagrelor, these will be discontinued/withheld and they will be withdrawn. Participants who receive at least one dose of IMP or endotoxin will be followed up by telephone 10-14 days after withdrawal.

As all participants will be taking ticagrelor at some stage during the study, drugs that interact with its metabolism should be avoided. Strong inhibitors of CYP3A4 substantially increase plasma ticagrelor levels whereas strong inducers of CYP3A4 have the opposite effects. Consequently, strong CYP3A4 inhibitors (eg, ketoconazole, itraconazole, voriconazole, telithromycin, clarithromycin [but not erythromycin or azithromycin], nefazadone, ritonavir, saquinavir, nelfinavir, indinavir, atanazavir, or over 1 litre daily of grapefruit juice) should not be co-administered with ticagrelor as plasma levels of ticagrelor would be substantially increased. If regular treatment with such therapies is essential, then ticagrelor should be withheld and they should be withdrawn. Participants who receive at least one dose of IMP or endotoxin will be followed up by telephone 10-14 days after withdrawal.

Concomitant therapy with simvastatin or lovastatin at doses higher than 40 mg daily is not permitted since ticagrelor significantly increases the levels of these statins and theoretically therefore may increase the risk of myopathy. There are no restrictions to other statin therapies (ie, doses of simvastatin or lovastatin \leq 40 mg daily or any dose of any other statin is permitted) but if a participant fails to meet the eligibility criteria for the study (section 6) at the next check (visit 3, 6 or 7), they will be withdrawn if the visit cannot be postponed. Standard monitoring of patients for possible statin-associated myopathy should be carried out.

Co-administration of ticagrelor with CYP3A substrates with a narrow therapeutic index (e.g. cyclosporine and quinidine) should be avoided.

Co-administration of ticagrelor with strong inducers of CYP3A should also be avoided (e.g. rifampin/rifampicin, rifabutin, phenytoin, carbamazepine, phenobarbital).

If regular treatment with such therapies becomes essential during the study medication period then they will be withdrawn from the study. Participants who receive at least one dose of IMP or endotoxin will be followed up by telephone 10-14 days after withdrawal.

Non-steroidal anti-inflammatory drugs (NSAIDs)

NSAIDs may affect the antiplatelet and immunomodulatory effects of aspirin whilst increasing the risk of gastric irritation/ulceration and renal impairment. Levels of arachidonic acid metabolites may also be affected. Requirement for regular treatment with an NSAID at enrolment meets the exclusion criteria of the study. Treatment with NSAIDs during the study period is discouraged. COX2 inhibitors are prohibited in combination with study medication. Paracetamol is safe in combination with both aspirin and ticagrelor and therefore will be the recommended analgesic/antipyretic agent if required. In the case of a participant requiring treatment with an NSAID/paracetamol/COX2 inhibitor, if they fail to meet the eligibility criteria for the study (section 6) at the next check (visit 3, 6 or 7), they will be withdrawn if the visit cannot be postponed. Participants who receive at least one dose of IMP or endotoxin will be followed up by telephone 10-14 days after withdrawal.

Other anti-inflammatory/immunomodulatory drugs

Oral, topical or inhaled corticosteroids; disease-modifying anti-rheumatic drugs; immunosuppressants; chemotherapy drugs; oral or topical antihistamines: In the case of a participant requiring regular treatment with these agents, if they fail to meet the eligibility criteria for the study (section 6) at the next check (visit 3, 6 or 7), they will be withdrawn if the visit cannot be postponed Participants who receive at least one dose of IMP or endotoxin will be followed up by telephone 10-14 days after withdrawal.

Diuretics

Diuretics, including loop (eg. furosemide, bumetanide), thiazide (eg. bendroflumethiazide, indapamide) and potassium-sparing agents (eg. spironolactone, eplerenone, amiloride), exert effects on renal prostaglandin synthesis and therefore may interfere with urinary prostaglandins. If a requirement for regular diuretic treatment develops during the study, a participant who fails to meet the eligibility criteria for the study (section 6) at the next check (visit 3, 6 or 7), will be withdrawn if the visit cannot be postponed. Those who receive at least one dose of IMP or endotoxin will be followed up by telephone 10-14 days after withdrawal.

ACE inhibitors/Angiotensin receptor blockers

ACE inhibitors and angiotensin receptor blockers can affect renal prostaglandin production. If a participant fails to meet the eligibility criteria for the study (section 6) at the next check (visit 3, 6 or 7), they will be withdrawn if the visit cannot be postponed but followed up by telephone at 10-14 days after withdrawal.

Parenteral anticoagulants

In the event of an indication for parenteral anticoagulation developing, the participant will be withdrawn from the study but participants who receive at least one dose of IMP or endotoxin will be followed up by telephone 10-14 days after withdrawal.

Glycoprotein IIb/IIIa antagonists

In the event of an indication for an agent in this group developing, the participant will be withdrawn from the study. Participants who receive at least one dose of IMP or endotoxin will be followed up by telephone 10-14 days after withdrawal.

Oral anticoagulants

The use of oral anticoagulants (e.g. warfarin, apixaban, rivaroxaban, dabigatran) in combination with study medication is prohibited. If oral anticoagulation is considered essential during the intended course of the study, the participant will be withdrawn from the study. Participants who receive at least one dose of IMP or endotoxin will be followed up by telephone 10-14 days after withdrawal.

Fibrinolytic agents

Treatment with fibrinolytic agents should be avoided whenever possible during treatment with study medication. If a participant is to receive a fibrinolytic agent the participant will be withdrawn from the study. Participants who receive at least one dose of IMP or endotoxin will be followed up by telephone 10-14 days after withdrawal.

Other drugs

If regular treatment with any other prescribed or over-the-counter systemic or topical medication becomes required after randomisation, if a participant fails to meet the eligibility criteria for the study (section 6) at the next check (visit 3, 6 or 7), they will be withdrawn if the visit cannot be postponed.

8.10 Trial restrictions

Whilst undergoing sampling during visits 3 and 7, subjects will take a light breakfast before 8 am then remain nil by mouth until 2 hours post-endotoxin.

Surgery and other invasive procedures

If surgery or another procedure becomes necessary during the study medication period, study medication should be stopped and the participant will be withdrawn from the study. Participants who receive at least one dose of IMP or endotoxin will be followed up by telephone 10-14 days after withdrawal.

The effects of aspirin, but not ticagrelor, may be reversed by platelet transfusion, which might be considered in the event of life-threatening bleeding.

Intercurrent illness

In the event of a participant developing an intercurrent illness after randomisation, for example a viral upper respiratory tract infection, medication periods or endotoxin injections may be postponed, at the discretion of the investigator, until resolution of the illness. A file note should be generated and placed in the trial master file.

8.11 Assessment of compliance with treatment

Compliance will be assessed at the end of each treatment period by counting the remaining sachets of aspirin (aspirin lysine) returned by the participant, and by direct observation of the participant taking the loading dose of ticagrelor and last dose of aspirin in each period, where applicable. Sachet counts will be carried out by the investigators and then cross-checked by the Pharmacy Department. Compliance will be recorded in the CRF.

8.12 Name and description of each Non-Investigational Medicinal Product (NIMP)

Although not a medicinal product, in this study we are additionally administering **sterile bacterial endotoxin**, 2 ng/kg intravenously. As a challenge agent, this is classified as a NIMP, as per European Commission Guidance Document SANCO/C/8/SF/cg/a.5.001(2011)332855. This will be reconstituted with water for injection as per the manufacturer's instructions. Endotoxin specifically designed for human challenge studies will be obtained from [name], National Institutes of Health, Bethesda, USA. Endotoxin will be securely stored separately in cold storage within the Cardiovascular Research Unit, Northern General Hospital. The temperature of the storage environment will be monitored by recording a daily maximum and minimum temperature log (with the exception of weekends). The allowable temperature range will be 2 to 8 degrees Celsius. An accountability log to track each vial will be kept in the trial master file. Endotoxin will be prescribed by a medically-qualified investigator on a Sheffield Teaching Hospitals Drug Administration Record. Administration will be recorded on the same chart.

9 PHARMACOVIGILANCE

9.1 Definitions

Term	Definition
Adverse Event (AE)	Any untoward medical occurrence in a participant to whom a medicinal product has been administered, including occurrences which are not necessarily caused by or related to that product.

Adverse Reaction (AR)	
An untoward and unintended response in a participant to an investigational medicinal product which is related to any dose administered to that participant.
 
The phrase "response to an investigational medicinal product" means that a causal relationship between a trial medication and an AE is at least a reasonable possibility, i.e. the relationship cannot be ruled out.
 
All cases judged by either the reporting medically qualified professional or the Sponsor as having a reasonable suspected causal relationship to the trial medication qualify as adverse reactions. It is important to note that this is entirely separate to the known side effects listed in the SmPC. It is specifically a temporal relationship between taking the drug, the half-life, and the time of the event or any valid alternative aetiology that would explain the event.

Serious Adverse Event (SAE)	
A serious adverse event is any untoward medical occurrence that:
 
 • results in death • is life-threatening • requires inpatient hospitalisation or prolongation of existing hospitalisation • results in persistent or significant disability/incapacity • consists of a congenital anomaly or birth defect 
Other 'important medical events' may also be considered serious if they jeopardise the participant or require an intervention to prevent one of the above consequences.
 
NOTE: The term "life-threatening" in the definition of "serious" refers to an event in which the participant was at risk of death at the time of the event; it does not refer to an event which hypothetically might have caused death if it were more severe.

Serious Adverse Reaction (SAR)	
An adverse event that is both serious and, in the opinion of the reporting Investigator, believed with reasonable probability to be due to one of the trial treatments, based on the information provided.

Suspected Unexpected Serious Adverse Reaction (SUSAR)	
A serious adverse reaction, the nature and severity of which is not consistent with the information about the medicinal product in question set out in the reference safety information:
 
 • SmPC for aspirin (aspirin lysine) • SmPC for ticagrelor

9.2 Operational definitions for (S)AEs

Adverse events and reactions will be recorded and reported from randomisation to 10 days after visit 3 (first endotoxin injection day), and from visit 6 (start of period 2) to 10 days after visit 7 (second endotoxin injection day). Thus, adverse events occurring in the break between the first and second medication periods, excepting those originating in the 10 days after endotoxin injection, will not be recorded or reported.

All SAEs will be reported to the sponsor within 24 hours of the research team becoming aware of them. This will be using the sponsor's proforma which will be sent by email to a dedicated address provided

specifically for this purpose. A copy will be kept in the trial master file and the AE log will be completed. All SAEs will be reviewed at the regular trial management group meetings.

All other AEs not meeting the criteria for reporting as serious will be recorded in the CRF, with the exception of the following events which will not be reported, as they can be expected as a normal response to endotoxin:

- Abnormal body temperature, excepting if $>39^{\circ}\text{C}$ and $<34^{\circ}\text{C}$, unless this persists at 6 hours post-endotoxin or meets the criteria for reporting as an SAE.
- Change in pulse rate, excepting pulse rates of >140 bpm and <45 bpm or if meeting the criteria for SAE reporting.
- Change (increase or decrease) in systolic or diastolic blood pressure from baseline of <40 mmHg unless meeting the criteria for SAE reporting.
- Self-limiting symptoms wholly due to endotoxaemia, for example fever, rigors, general malaise, nausea, vomiting or headache, at the discretion of the investigator, unless meeting the criteria for SAE reporting.
- Alterations in leukocyte (or subset) counts, platelet count or C-reactive protein unless meeting the criteria for SAE reporting.

The investigators will assess the relatedness of adverse events to the IMPs (aspirin [aspirin lysine], ticagrelor) and NIMP (endotoxin).

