- **Prostanoids and Leukotrienes**
- Serum TXB₂: Baseline, pre-last medication dose, pre-endotoxin and 0.5, 1, 1.5, 2, 3, 4 and 6 hours post-endotoxin
- Urinary PGI-M: Baseline, pre-endotoxin and 1, 2, 4 and 6 hours post-endotoxin
- Urinary creatinine: Baseline, pre-endotoxin and 1, 2, 4 and 6 hours
- Serum PGE₂: Baseline, pre-endotoxin and 0.5, 1, 1.5, 2, 3, 4 and 6 hours post-endotoxin
- **Leucocyte phenotype and activation status**
- White blood cell count with differential leukocyte count: Baseline, pre-last medication dose, pre-endotoxin and 0.5, 1, 1.5, 2, 3, 4 and 6 hours post-endotoxin
- **Haemostasis**
- Bleeding time: Pre-endotoxin and 3 hours post-endotoxin
- **Platelet function tests**
- Light transmittance aggregometry (agonists: arachidonic acid 0.3 and 1 mmol/l, collagen 4 and 16 mg/ml, and ADP 20 μ mol/l): Baseline, pre-endotoxin and 3 hours post-endotoxin
- **Samples for storage**
- Plasma for storage: Baseline, pre-last medication dose, pre-endotoxin and 0.5, 1, 1.5, 2, 3, 4 and 6 hours post-endotoxin
- Serum for storage: Baseline, pre-last medication dose, pre-endotoxin and 0.5, 1, 1.5, 2, 3, 4 and 6 hours post-endotoxin
- DNA/RNA for storage: Baseline
- Urine for storage: Baseline, pre-endotoxin and 1, 2, 4 and 6 hours post-endotoxin

Details of fluid management

We anticipate that the total fluid load per volunteer will be 1000 ml over the 8 hours of the day at the NGH-CRF (250 ml preload and 750 ml infusion). The volunteers will also receive fluid boluses if required, which would be typically be in the range of 250-500 ml normal saline, given if mean arterial blood pressure is reduced by 20% or more or to maintain a systolic blood pressure over 100 mmHg and/or to relieve symptoms related to hypotension. Under normal circumstances, we would give a maximum of 1000 ml of

0.9% saline over 1 hour and a maximum of 2000 ml of 0.9% saline over the 8 hours of the day at the NGH-CRF.

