9.4 Responsibilities

Principal Investigator (PI) or delegate:

1. Checking for AEs and ARs when participants attend for treatment / follow-up.
2. Using medical judgement in assigning seriousness, causality and whether the event/reaction was anticipated using the Reference Safety Information approved for the trial.
3. Using medical judgement in assigning seriousness and causality and providing an opinion on whether the event/reaction was anticipated using the Reference Safety Information approved for the trial.
4. Ensuring that all SAEs are recorded and reported to the sponsor within 24 hours of becoming aware of the event and provide further follow-up information as soon as available. Ensuring that SAEs are chased with Sponsor if a record of receipt is not received within 2 working days of initial reporting.
5. Ensuring that AEs and ARs are recorded and reported to the sponsor in line with the requirements of the protocol.

Chief Investigator (CI, in this single-site study the same individual as the PI) or delegate:

1. Clinical oversight of the safety of patients participating in the trial, including an ongoing review of the risk / benefit.
2. Using medical judgement in assigning whether an event/reaction was anticipated or expected in line with the Reference Safety Information.
3. Immediate review of all SUSARs.
4. Assigning Medical Dictionary for Regulatory Activities (MedDRA) or Body System coding to all SAEs and SARs.
5. Preparing the clinical sections and final sign off of the Development Safety Update Report (DSUR).

Sponsor: (NB where relevant these can be delegated to CI)

1. Collection and verification of AEs, ARs, SAEs, SARs and SUSARs according to the trial protocol.

2. Expedited reporting of SUSARs to the Competent Authority (MHRA) and REC within required timelines.
3. Checking for (annually) and notifying PIs of updates to the Reference Safety Information for the trial.
4. Preparing standard tables and other relevant information for the DSUR in collaboration with the CI and ensuring timely submission to the MHRA and REC.

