10.6 Interim analysis and criteria for the premature termination of the trial

After discussion between the investigators and the Sponsor, face-to-face participant study visits were halted on 17th March 2020 due to the unprecedented circumstances arising during the coronavirus disease 2019 (Covid-19) pandemic. It was considered by the investigators that the results of the study may have important implications for the management of cardiovascular disease patients who contracted Covid-19 in terms of optimal antiplatelet medication, in view of the morbidity and mortality in Covid-19 associated with dysregulated inflammatory response. It was noted that the recruitment and study activities to date had reached the level that had originally been planned for the study, as per the application funded by the British Heart Foundation. Given the uncertainty regarding restarting the trial, the need to preserve healthcare resources and to limit face-to-face encounters, the investigators and Sponsor decided that an interim analysis should be performed.

Sample size for interim analysis

Data from all participants who have completed visit 3 (first endotoxin day) will be included in the interim analysis. This is expected to include 46 participants who have completed visit 3, 37 of whom have completed the whole study giving a total of 83 endotoxin day visits, anticipated to be split into approximately equal numbers receiving each of the eight study treatment regimens.

Statistical procedure for interim analysis

The primary endpoint of the interim analysis will be plasma TNF- α measured at 2 hours after endotoxin administration assessed between aspirin treatment groups (control vs. 20 mg BD vs. 75 mg OD vs. 300 mg OD, without ticagrelor) using one-way ANOVA.

Should this demonstrate a significant difference between the groups ($p<0.05$), the following pre-specified pairwise comparisons will be performed, in hierarchical fashion:

300 mg OD vs. no aspirin

then, if significant ($p<0.05$)

75 mg OD vs. no aspirin

then, if significant ($p<0.05$)

300 mg OD vs 20 mg BD

then, if significant ($p<0.05$)

75 mg OD vs 20 mg BD

then, if significant ($p<0.05$)

20 mg BD vs no aspirin

Other analyses will be exploratory.

Criteria for premature termination

The trial shall be prematurely terminated if the primary interim analysis demonstrates a statistically significant ($p<0.05$) effect of aspirin dosing on plasma TNF- α two hours after endotoxin injection.

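### The AE exemption for blood-pressure changes under 40 mmHg has no exception for treated hypotension, so episodes given a fluid bolus can go without an AE entry

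*Protocol*

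**What the plan says.** Protocol section 9.2 sends non-serious AEs to the CRF, "with the exception of the following events which will not be reported, as they can be expected as a normal response to endotoxin". One listed item is "Change (increase or decrease) in systolic or diastolic blood pressure from baseline of <40 mmHg unless meeting the criteria for SAE reporting". Meeting the SAE criteria is that item's only exception. The neighbouring items are tighter: the pulse item has an absolute floor of 45 bpm, and the temperature item becomes reportable if the abnormality is still present at 6 hours.

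The fluid-management text in section 7.7 states the planned volume: "We anticipate that the total fluid load per volunteer will be 1000 ml over the 8 hours of the day at the NGH-CRF". Extra boluses, typically 250-500 ml, are "given if mean arterial blood pressure is reduced by 20% or more or to maintain a systolic blood pressure over 100 mmHg", and also for symptoms of hypotension. Nothing in the protocol or SAP says that giving a bolus makes the episode a recordable AE.

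Three other places bear on this:
- Section 9.1: important medical events "may also be considered serious if they jeopardise the participant or require an intervention to prevent one of the above consequences".
- Section 9.2, on causality: "The investigators will assess the relatedness of adverse events to the IMPs" and to endotoxin.
- Section 9.4, on the investigator's duty: "Ensuring that AEs and ARs are recorded and reported to the sponsor in line with the requirements of the protocol".

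**The concern.** The reporting limit and the treatment trigger were set separately, and the treatment trigger is usually the lower of the two. A participant can have a fall large enough for the protocol to call for treatment, receive up to half a litre of extra saline, and still have an event that 9.2 tells the site not to report. Relatedness is assessed for adverse events, so without an AE entry there is no place where a causal link to ticagrelor, aspirin or endotoxin is considered.

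The stated reason for the exemption also fits this event less well than it fits fever or malaise. Section 2.1 describes hypotension after endotoxin as rare, while the SmPC table in the same section lists hypotension among common ticagrelor reactions. Sections 7.3 and 8.9 confirm that every participant is due a 180 mg ticagrelor loading dose, 1 hour before one of the two challenges. The SmPC table describes ticagrelor use in general and not a single loading dose, so it shows only that a drug cause is plausible.

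At stake is the completeness of the AE data for healthy volunteers. AE reporting is a planned output with its own analysis set (section 10.7 of both documents). No efficacy result depends on it.

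**Working it through.** **Inputs.** Exemption limit: 40 mmHg (9.2). Bolus triggers: MAP down 20% or more, or systolic to be kept over 100 mmHg (7.7). Eligible resting pressure: 105/65 to 150/90 (6.2, item 5). The 120/75 row is an assumed typical baseline. Pressures on the challenge day may differ from screening.

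**MAP trigger.** MAP = (systolic + 2 × diastolic)/3. Four patterns of fall, each solved for a MAP fall of 0.2 × MAP:
- equal falls of x: MAP falls by x, so x = 0.2 × MAP
- diastolic falls half as much as systolic: MAP falls by (x + 2 × x/2)/3 = 2x/3, so x = 1.5 × 0.2 × MAP
- both fall in proportion: 20% of each
- systolic alone: MAP falls by x/3, so x = 3 × 0.2 × MAP

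| Baseline | MAP | Equal falls | Systolic fall, diastolic half as much | Proportional falls | Systolic alone |
|---|---|---|---|---|---|
| 105/65 | 78.3 | 15.7 | 23.5 | 21/13 | 47 |
| 120/75 | 90 | 18 | 27 | 24/15 | 54 |
| 150/90 | 110 | 22 | 33 | 30/18 | 66 |

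Every pattern except the purely systolic one meets the MAP trigger inside the 40 mmHg limit.

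**Systolic trigger.** Systolic 100 is reached by a fall of 5 from 105, 20 from 120 and 39 from 139, all under 40. From 140 the fall is 40, which is recordable. So the reporting limit comes first only for wholly or mainly systolic falls from a baseline of 140 or more. From 150/90, for instance, a systolic fall of 40 gives a 22 mmHg MAP fall only if diastolic falls by 13: (40 + 2 × 13)/3 = 22.

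**Example.** From 120/75 to 95/60 the fall is 25/15. MAP goes from 90 to (95 + 120)/3 = 71.7, and (90 − 71.7)/90 = 20.4%. Both triggers are met, neither component falls by 40, and the event is exempt unless judged serious.

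**Exposure.** Section 10.6 expects 46 participants past their first challenge, "37 of whom have completed the whole study giving a total of 83 endotoxin day visits": 46 + 37 = 83. The 37 completers have one ticagrelor day each and the other 46 − 37 = 9 have none or one, so 37 to 46 of the 83 days involved ticagrelor. Full recruitment gives 72 × 2 = 144 days, 72 of them with ticagrelor. At most 144 − 83 = 61 days remain, of which 72 − 46 = 26 to 72 − 37 = 35 would be with ticagrelor. If the trial stops at the interim, none remain. These are exposure days and not events; the documents give no rate of bolus use.

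**The case against.** The strongest reply is that nothing here conflicts. A cautious management trigger and a reporting threshold serve different purposes and need not coincide. Saline given because a systolic pressure of 105 drifted to 100 is hardly an untoward event. That stands as a point about purpose, and the triggers in 7.7 need no change. It does not explain why an episode that was actually treated should leave no AE entry.

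Second, other routes may catch the event. Serious cases are reported, but the important-medical-event route is a judgement, and a routine bolus need not qualify. Symptoms are exempt only if they are self-limiting and put down entirely to endotoxin, so symptoms that might be due to ticagrelor stay recordable; a fall without symptoms has none to record.

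Third, 9.1 counts any case with a reasonably suspected link to trial medication as an adverse reaction. A reader might infer from 9.2 that ticagrelor-induced hypotension is bound to be lost. The documents do not support that: an investigator who suspects ticagrelor could record a reaction despite the exemption. The endotoxin wording at the head of the list reads as a reason and not as a condition, so 9.2 does not require the question to be asked, and the point remains arguable.

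Fourth, vital signs are taken on a fixed schedule from 5 minutes to 6 hours on both challenge days, so pressures with and without ticagrelor can be compared within participants. This stands and limits the loss. The readings carry no relatedness assessment, and the documents do not show whether the CRF holds bolus volume.

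**Conclusion.** The gap is real but narrow. Section 9.2 can leave treated, non-serious and mainly asymptomatic hypotension without an AE entry or a relatedness assessment, because the bolus triggers are reached inside the 40 mmHg limit for most eligible baselines and patterns of fall. The threshold arithmetic is firm, subject to challenge-day pressures being near the screening range. The number of affected episodes is unknown. If hypotension after endotoxin is as rare as section 2.1 says, it may be very small.

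Two stronger inferences should be resisted. One is that AE data from the 83 completed days are known to be deficient. Section 10.6 says nothing about AE recording on those days, and the documents do not show which version of 9.2 was then in force. The other is that 61 days can still be put right. The interim stopping rules could make that zero.

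This is a low-severity, inexpensive improvement to the safety data, with no bearing on the efficacy analyses.

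**What to change.** Add to the end of the blood-pressure item in 9.2: *or if a fluid bolus (beyond the planned infusions) or other treatment is given for hypotension*. Record each such episode as an AE, with relatedness to ticagrelor, aspirin and endotoxin. Leave untreated changes under 40 mmHg exempt and the 7.7 triggers as they are.

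Apply the clause to whatever challenge days remain. For the roughly 83 completed days, look back for saline beyond the planned 1000 ml where records allow; otherwise state in the report which recording rule applied to them.

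The cost is one clause, one CRF entry per treated episode and a small look-back that may depend on records outside the CRF. Reported hypotension counts would rise slightly, and the report should say why.
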